3.4.2 Dose delay

- Bintrafusp alfa should be withheld for Grade \geq 2 epistaxis or any Grade \geq 2 toxicity possibly attributed to the study agent until resolution to Grade \leq 1 unless the toxicity in the opinion of the investigator is not clinically relevant or can be medically managed with minimal risk to the participant. Should a clinically relevant grade 2 or 3 toxicity persist for more than 4 weeks, consideration should be given to discontinuing treatment at the discretion of the investigator.
- Laboratory abnormalities which are clinically non-significant and/or unrelated to the agent in the judgement of the investigator, will not lead to dose delays.
- Grade 3 fatigue, headache, nausea, emesis that resolve to Grade \leq 1 with appropriate medical management will not lead to dose delays.
- Management recommendations for infusion-related adverse reactions are found in **Appendix B**: Recommendations for Management of IRRs and AEs, Table A Management of Infusion-related Reactions and should be followed along with institutional standards.
- Immune-related adverse reactions (irAE) should lead to treatment modifications and management per the summarized NCCN recommendations found in **Appendix B**: Recommendations for Management of IRRs and irAEs, Table B Management of immune-related adverse events. Investigators may refer to the relevant guidelines available by ASCO (62), SITC (63), NCCN (64), and ESMO (65).
- For non-medical logistical reasons, unrelated acute illnesses, or palliative radiation, scheduled assessments and dosing can be delayed up to 2 months. Following this interval treatment may resume, and where at all possible, dosing should be restarted to keep in line with the original treatment schedule.

- Local tumor flare phenomenon defined as local pain, irritation, or rash localized at sites of known or suspected lesions will not be considered adverse event or lead to dose interruptions.

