3.2 STUDY ACCRUAL STOPPING RULE

Once the 6th participant had reached the 6 months follow up period (or potentially would have reached the 6 months follow-up if the participant died prior to the 6 months follow-up), the study will be halted for a DSMB review of the available data if more than 85% of participants have PD \leq 6 months following the first dosage. In the absence of literature information on response rates with other treatments in the second-line, his threshold comes from the considerations of acceptable response rates used for sample size determination in Section [10.2](#).

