6. Subsequent Post-treatment follow-up: Every 3 months (+/- 2 weeks), starting after the safety visit for the first year, followed by every 6 months (+/- 4 weeks) for years 2-5, and then annually (+/- 6 weeks) thereafter at the discretion of the investigator. Follow-ups may be done by phone/email or by clinic visit at the discretion of the investigator. Follow-up via telephone/email will include survival, adverse events, and assessment of further tumor therapy; furthermore, routine outside blood, urine, and imaging results may be collected and used for analysis at the discretion of the investigator. Any other evaluations and tests should be performed as clinically indicated. Participants who have not progressed on treatment will be scanned until progression. Those that completed the previous 26-doses course and have progression will be invited for an additional course (26 doses) at the time of progression.
7. Bintrafusp alfa administered IV at flat dose of 1,200 mg.
8. As indicated in Section **12.3**, all subjects will be offered the opportunity to complete an NIH advance directive form. This should be done preferably at baseline but can be done at any time during the study as long as the capacity to do so is retained. The completion of the form is strongly recommended but is not required.
9. Every 6 weeks.
10. Imaging (Section **6.3**) will be performed every 8 weeks (+/- 1 week). In the event of a PR or CR, tumor imaging assessments may be performed every 3 months (+/- 2 weeks) at the discretion of the investigator. Tumor assessment should be continued beyond end of treatment in participants who have not experienced PD until they experience PD in order to assess PFS. Additional imaging to be performed at the investigator's discretion. Imaging performed in outside facilities maybe utilized in the case of travel restrictions or delays, airport closures, inclement weather, family responsibilities, security alerts and government holidays, etc. Nuclear bone scan or imaging may be done for individuals with known/suspected bone lesions at screening; in these cases bone scans should be done in follow-up for response assessments.
11. Optional biopsies: at baseline (within 2 weeks prior to first treatment) and within 2 weeks of first imaging restaging; optional biopsy at/near progression, where clinically feasible.

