6.3 RESPONSE ASSESSMENT

For the purposes of this study, during the study participants should be re-evaluated for response every 8 weeks (+/- 1 week), according to the [Study Calendar](#).

The Investigator may perform scans in addition to a scheduled trial scan for medical reasons or if the Investigator suspects PD.

Tumor assessments may include the following evaluations: physical examination (with photograph and measurement of skin lesions, as applicable); cross-sectional imaging using computed tomography (CT) or magnetic resonance imaging (MRI) scan of the skull base, neck, chest, abdomen, and pelvis; nuclear bone scan for subjects with known/suspected bone lesions; and CT of the skull base and MRI of brain (at baseline and follow ups as clinically warranted based on symptoms/findings per investigator discretion). The preferred method of disease assessment is CT with contrast. If CT with contrast is contraindicated, CT of the chest without contrast and MRI scan of the skull base, neck, abdomen/pelvis is preferred.

Radiologic imaging: Brain MRI/CT at the baseline and if needed at follow ups. CT scan of skull base, neck, chest, abdomen, and pelvis. or MRI.

In addition, PET (FDG or Dotatate) scan will be acquired at the time of first treatment response evaluation, and at/near radiographic progression, where clinically feasible. PET scan may also be acquired per investigator discretion to characterize metabolic activity of lesions (target/non-target/new) beyond cross-sectional measurement-based response categories, such as in cases of, discordant response among lesions, durable partial response, or other indeterminate radiological changes.

For each participant, the Investigator will designate 1 or more of the following measures of tumor status to follow for determining response: CT or MRI images of primary and / or metastatic tumor masses, physical examination findings, and the results of other assessments.

The measure(s) to be chosen for sequential evaluation during the trial have to correspond to the measures used to document the progressive tumor status that qualifies the subject for enrollment.

Post-baseline response assessments should follow the lesions identified at baseline. The same modality of assessment (e.g., CT) used to identify/evaluate lesions at baseline should be used throughout the course of the study unless subject safety necessitates a change (e.g., allergic reaction to contrast media).

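### Section 3.4.2 allows scheduled assessments as well as dosing to slip by up to 2 months, conflicts with the 8-week imaging rule, and can date progression late

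*Combined protocol and SAP*

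**What the plan says.** The delay allowance is in Section 3.4.2: "For non-medical logistical reasons, unrelated acute illnesses, or palliative radiation, scheduled assessments and dosing can be delayed up to 2 months". It treats assessments and doses together and does not mention imaging. The Study Calendar (3.7) lists tumor imaging in its assessments block, so a plain reading includes it.

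Two other places set the imaging interval. In Section 6.3, "participants should be re-evaluated for response every 8 weeks (+/- 1 week" of the scheduled date, and in calendar footnote 10 imaging "will be performed every 8 weeks (+/- 1 week" of it. Neither makes an exception for held or delayed doses.

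The documents do provide some flexibility for imaging:

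- Section 6.3: "The Investigator may perform scans in addition to a scheduled trial scan for medical reasons or if the Investigator suspects PD".
- Footnote 10: "Imaging performed in outside facilities maybe utilized in the case of travel restrictions or delays", followed by a list of similar obstacles.
- Footnote 10, after a PR or CR: "tumor imaging assessments may be performed every 3 months (+/- 2 weeks) at the discretion of the investigator".
- Footnote 3 allows three-monthly assessments for a durable response after one year, and Section 6.3 lets a participant skip a scan that falls due soon after a confirmation scan.

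Two analyses depend on the date of progression. Section 10.4.2 analyses PFS by Kaplan-Meier from first treatment and has no rule for late or missed scans. Section 3.2 applies once the sixth participant reaches 6 months: "the study will be halted for a DSMB review of the available data if more than 85% of participants have PD" within 6 months of the first dose.

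**The concern.** Radiographic progression is dated by the scan that shows it. A postponed scan therefore moves the recorded date later, whatever the tumor was doing in the meantime. Two investigators could both follow the protocol and restage similar participants about two months apart.

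Palliative radiation is the reason that deserves most attention. It may accompany symptomatic progression, but Section 4.1 says that needing it does not count as PD, and Section 3.9.1 lets treatment continue. In such a participant, documented PD depends on the scan that 3.4.2 appears to let slip. The delay may then be informative.

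What is at stake is the PFS curve and the 6-month count in Section 3.2. In a cohort of 21, each participant is 1/21 = 4.8 percentage points of the curve before any censoring.

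**Working it through.** **The plan's own figure.** No sample size, event count or power is given for PFS. The one relevant design figure is the 54.0% early-termination probability in Section 10.2: 0.95^12 = 0.5404, which reproduces. Exact type I error is 0.0804 and power 0.8033, within the stated limits of 0.10 and 0.80. No scan interval enters these calculations, so the point leaves them unchanged.

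**Scan timing.** Inputs: delay up to 2 months (3.4.2); interval 8 weeks, window 1 week either way (6.3, footnote 10); cut-off 6 months (3.2). With a month of 30.4375 days:

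- 2 months = 2 × 30.4375 / 7 = 8.7 weeks; 6 months = 26.1 weeks.
- Longest gap inside the window: one scan a week early, the next a week late, 8 + 2 = 10 weeks.
- Gap with a full delay: 8 + 8.7 = 16.7 weeks, or 17.7 if the previous scan was a week early.
- Week-24 scan: 24 + 8.7 = week 32.7, past 26.1. Any delay above 26.1 − 24 = 2.1 weeks is enough.
- Week-16 scan: 16 + 8.7 = week 24.7, still inside 6 months.

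For a single delay, then, only PD first visible at week 24 crosses the cut-off.

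**Size across a cohort.** The documents give neither a PFS assumption nor a delay frequency, so both are assumed here. Let true progression be exponential with median m weeks, and let a share f of detecting scans be delayed by the full 8.7 weeks. The mean recorded progression time then rises by f × 8.7: 0.9, 2.2 and 4.3 weeks at f = 10%, 25% and 50%. Ignoring deaths, the share with PD recorded by 6 months is

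(1 − f) × (1 − 2^(−24/m)) + f × (1 − 2^(−16/m)).

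| Assumed median (weeks) | f = 0 | 10% | 25% | 50% |
|---|---|---|---|---|
| 8 | 87.5% | 86.3% | 84.4% | 81.3% |
| 12 | 75.0% | 73.5% | 71.3% | 67.7% |
| 16 | 64.6% | 63.2% | 61.0% | 57.3% |
| 26 | 47.3% | 46.0% | 44.1% | 41.0% |

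Delays unrelated to progression push the same way. By simulation with m = 16, delaying 10%, 25% or 50% of all scans at random moves the mean recorded time from 27.3 weeks to 28.1, 29.2 and 30.5.

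**Section 3.2 rule.** The denominator is not fixed. If six participants are counted, 5/6 = 83.3% does not exceed 85%, so all six must have PD, and one postponed week-24 scan turns 6/6 into 5/6. With seven counted, 6/7 = 85.7% still triggers; with eight, 7/8 = 87.5% does and 6/8 = 75% does not. For six independent participants the chance of triggering is the tabulated share to the sixth power. At m = 8, this is 0.875^6 = 44.9% with no delay and 0.844^6 = 36.1% at f = 25%. At m = 16, it is 0.646^6 = 7.3% and 0.610^6 = 5.1%.

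**The case against.** The strongest reply is that the allowance sits under a dose-delay heading and speaks of assessments in general, whereas 6.3 and footnote 10 are specific to imaging. Reading the specific rule as governing is at least as natural. A reader might infer that 3.4.2 overrides the imaging calendar; the documents do not support that, because no order of precedence is stated. What remains is an unresolved conflict.

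A reader might also infer that scans can be put off just when progression is suspected. The text does not say so. Two of the three reasons are by their wording not disease-driven, and 6.3 permits an extra scan on suspicion of PD. Palliative radiotherapy may treat baseline disease, and Section 4.1 confines it to non-target lesions. These points weaken the link to progression. They do not remove the problem: the extra scan is optional, footnote 10's examples for outside imaging name neither acute illness nor palliative radiation, and random delay also lengthens recorded time.

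Loss of response confirmation is another tempting inference. It is weak: 6.3 and Appendix C set a minimum interval of 4 weeks and no maximum, so a later scan can still confirm.

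Finally, the consequences are limited. PFS is a secondary, single-arm, descriptive endpoint; deaths count on their own date; and the 3.2 rule calls for a DSMB review, not termination. All of this stands.

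**Conclusion.** The conflict is real and should be resolved. Sections 3.4.2 and 6.3 and footnote 10 cannot all be followed when an assessment is postponed for a 3.4.2 reason beyond the one-week imaging window. If 3.4.2 is taken to cover imaging, a restaging gap can reach about 16.7 weeks and recorded progression can be late by up to about 8.7 weeks per delayed detecting scan. For PD first visible at week 24, a delay of more than 2.1 weeks removes it from the 6-month count.

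A flat statement that the clause inflates PFS goes too far: it can lengthen recorded PFS, by an amount that depends on how often the clause is used. The cohort figures rest on assumed exponential progression, assumed medians of 8 to 26 weeks, full-length delays and assumed delay shares. The 3.2 result further assumes that six participants are counted. The response-rate design and its error rates do not change.

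**What to change.** Reconcile the passages by adding to Section 3.4.2 wording such as: *This allowance does not move tumor imaging. Imaging stays on the protocol calendar counted from first dose, whether or not doses are delayed, except where the protocol already permits another interval.* Name those exceptions: the three-monthly option after PR or CR (footnote 10), the durable-response schedule (footnote 3) and the scan that may be skipped after a confirmation scan (6.3). Without them the new sentence would create fresh conflicts and label permitted scans as deviations.

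Extend footnote 10's outside-facility imaging to the reasons listed in 3.4.2, and record other out-of-window scans as deviations. A line in Section 10.4.2 on how PFS treats late or missed scans would complete the change.

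The dosing allowance is left as it stands. Its relation to the administration window in footnote 3 also needs reconciling, on which this point takes no position.

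The cost is a short amendment with no added scheduled scans. The downside is small: some scans at outside facilities, and occasional late scans in acutely ill participants recorded as deviations.

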3.4 DOSE MODIFICATIONS

3.4.1 Discontinuation

Treatment with bintrafusp alfa will be discontinued in participants experiencing specific adverse events; subjects will remain on study for follow up of survival. Treatment will be discontinued in any participant in the case of:

- Any Grade 4 or higher adverse drug reactions (ADRs) graded according to NCI CTCAE v5.0 and assessed as possibly related to that agent by the Investigator, except for laboratory values that are asymptomatic or resolve to Grade ≤ 1 or baseline grade within 7 days without medical intervention.

- Any Grade 3 ADRs possibly attributed to any agent **except** for any of the following:
 - Transient (\leq 48 hours) Grade 3 nausea and vomiting, headache, flu-like symptoms, fever, controlled with appropriate medical management.
 - Tumor flare phenomenon defined as local pain, irritation, or rash localized at sites of known or suspected tumor.
 - Endocrinopathy that can be medically managed with hormone replacement.
 - Keratoacanthoma and squamous cell carcinoma of the skin. Suspicious skin lesions will be evaluated by dermatology and managed per recommendations (**Appendix B**: Recommendations for Management of IRRs and AEs, Table C), including potential removal of the lesion.
 - Grade 3 laboratory test abnormalities that resolve to Grade \leq 1 or to baseline Grade within 7 days with appropriate medical management or Grade 3 laboratory test abnormalities that are determined not to be clinically significant or asymptomatic.
 - Grade 3 anemia with Hgb <8.0 g/dL that is clinically manageable with PRBC transfusions does not require treatment discontinuation.
 - Any Grade 3 ADR which in the opinion of the investigator is not clinically relevant or can be managed with minimal risk to the participant (e.g. placement of a pleural catheter for recurrent inflammatory pleural effusions).

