6 DATA COLLECTION AND EVALUATION

6.1 DATA COLLECTION

The PI will be responsible for overseeing entry of data into a 21 CFR Part 11-compliant data capture system provided by the NCI CCR and ensuring data accuracy, consistency and timeliness. The principal investigator, associate investigators/research nurses and/or a contracted data manager will assist with the data management efforts. Primary and final analyzed data will have identifiers so that research data can be attributed to an individual human subject participant.

All adverse events, including clinically significant abnormal findings on laboratory evaluations, regardless of severity, will be followed until return to baseline or stabilization of event.

Document AEs from the first study intervention, study day 1, through 28 days after the subject received the last product administration. After 28 days, only adverse events which are serious and related to the study investigational agent need to be recorded.

An abnormal laboratory value will be recorded in the database as an AE **only** if the laboratory abnormality is characterized by any of the following:

- Results in discontinuation from the study
- Is associated with clinical signs or symptoms
- Requires treatment or any other therapeutic intervention
- Is associated with death or another serious adverse event, including hospitalization.
- Is judged by the Investigator to be of significant clinical impact
- If any abnormal laboratory result is considered clinically significant, the investigator will provide details about the action taken with respect to the test drug and about the participant's outcome.

End of study procedures: Data will be stored according to HHS, FDA regulations, and NIH Intramural Records Retention Schedule as applicable.

Loss or destruction of data: Should we become aware that a major breach in our plan to protect subject confidentiality and trial data has occurred, this will be reported expeditiously per requirements in Section [7.2.1](#).

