8 SPONSOR PROTOCOL / SAFETY REPORTING

8.1 DEFINITIONS

8.1.1 Adverse Event

Any untoward medical occurrence in a participant or clinical investigation subject administered a pharmaceutical product and which does not necessarily have a causal relationship with this treatment. An adverse event (AE) can therefore be any unfavorable and unintended sign (including an abnormal laboratory finding), symptom, or disease temporally associated with the use of a medicinal (investigational) product, whether or not related to the medicinal (investigational) product (ICH E6 (R2)).

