8.2 ASSESSMENT OF SAFETY EVENTS

AE information collected will include event description, date of onset, assessment of severity and relationship to study product and alternate etiology (if not related to study product), date of resolution of the event, seriousness and outcome. The assessment of severity and relationship to the study product will be done only by those with the training and authority to make a diagnosis and listed on the Form FDA 1572 as the site principal investigator or sub-investigator. AEs occurring during the collection and reporting period will be documented appropriately regardless of relationship. AEs will be followed through resolution.

SAEs will be:

- Assessed for severity and relationship to study product and alternate etiology (if not related to study product) by a licensed study physician listed on the Form FDA 1572 as the site principal investigator or sub-investigator.
- Recorded on the appropriate SAE report form, the medical record and captured in the clinical database.
- Followed through resolution by a licensed study physician listed on the Form FDA 1572 as the site principal investigator or sub-investigator.

For timeframe of recording adverse events, please refer to Section [6.1](#).

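### Section 3.4.2 denies adverse event status to local tumor flare at any grade, against 8.1.1, 6.1, 8.2 and 3.4.1, so local toxicity can be undercounted in the safety tables

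*Combined protocol and SAP*

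**What the plan says.** The last bullet of 3.4.2 (Dose delay) states that local tumor flare "will not be considered adverse event or lead to dose interruptions". It carries no limit by grade, duration or relatedness.

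Section 3.4.1 (Discontinuation) names the same event, "Tumor flare phenomenon defined as local pain, irritation, or rash localized at sites of known or suspected tumor", in its list of exceptions to the rule on "Any Grade 3 ADRs possibly attributed to any agent".

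Section 8.1.1 defines an AE to include "any unfavorable and unintended sign (including an abnormal laboratory finding), symptom, or disease temporally associated with the use of a medicinal (investigational) product". No causal link is required, and there is no exception for flare.

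On recording, 6.1 says "Document AEs from the first study intervention, study day 1, through 28 days after the subject received the last product administration", and 8.2 says "AEs occurring during the collection and reporting period will be documented appropriately regardless of relationship". Within that window the only events 6.1 filters out are certain laboratory abnormalities.

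Safety and tolerability is the first-listed secondary objective (1.1.2). Section 10.4.3 analyses it as the fraction of participants with each toxicity by grade and type, plus AE frequencies by grade.

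**The concern.** One sentence in a dosing section changes what counts as an AE, and the sections that govern AE capture do not acknowledge it. An investigator faced with new pain or rash at a lesion site can cite 3.4.2 for not recording it, or 8.1.1 for recording it.

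The flare definition rests only on a non-specific symptom and its location. Nothing in it separates flare from another drug reaction at the same site, so a drug-related local event could be labelled flare and left out.

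At stake is the completeness of the AE tables for a stated secondary objective in a small single-arm trial. There is no control arm in which the same omission would occur and offset it.

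**Working it through.** The plan states no figure on this point, so the main check is to compare the passages.

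| Section | Status given to flare | Limit or exception |
|---|---|---|
| 3.4.2, last bullet | Not an AE; no dose interruption | None by grade or relatedness |
| 3.4.1, Grade 3 rule | Listed among adverse drug reactions | Excused from discontinuation only |
| 3.4.1, Grade 4 rule | Not mentioned | Only certain laboratory values are excepted |
| 8.1.1 | Meets the AE definition as an unfavorable sign or symptom | No flare exception |
| 6.1 and 8.2 | Must be documented if an AE | Within the window, only a laboratory filter |
| 10.4.3 | Tabulated if recorded | No flare exclusion and no separate flare listing |

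**Step 1.** New pain, irritation or rash after dosing satisfies 8.1.1. Sections 6.1 and 8.2 then require it to be documented regardless of relationship. Section 3.4.2 says it is not an AE. Both cannot hold.

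**Step 2.** An exception to a Grade 3 adverse drug reaction rule presupposes that the event is a graded adverse drug reaction. So 3.4.1 and 3.4.2 also conflict.

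**Step 3.** Section 10.4.3 does not itself drop flare. Any loss occurs at recording, because an event never entered as an AE cannot be tabulated. Section 10.4.6 mentions participants' descriptions of symptomatic AEs, but the Study Calendar (3.7) lists no instrument for collecting them, so this cannot be relied on to recover flare.

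**Step 4, scale.** Section 10.3.1 makes all treated participants evaluable for toxicity. Section 10.2 sets a ceiling of 32 (21 checkpoint-naïve + 8 checkpoint-resistant + 3 inevaluable). On a flare-specific rate, one omitted participant is worth:

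- 1/32 = 3.1 points overall at the ceiling
- 1/29 = 3.4 points overall without the inevaluable allowance (21 + 8)
- 1/24 = 4.2 points in the checkpoint-naïve cohort if all 3 inevaluable participants fall there (21 + 3)
- 1/21 = 4.8 points in the checkpoint-naïve cohort at its target

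**Step 5, illustration only.** The documents give no flare incidence. For an assumed incidence f among N participants, with every flare omitted, expected omissions = N × f and P(at least one) = 1 − (1 − f)^N.

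| Assumed f | N = 21: expected, P(≥1) | N = 32: expected, P(≥1) |
|---|---|---|
| 2% | 0.4, 0.35 | 0.6, 0.48 |
| 5% | 1.1, 0.66 | 1.6, 0.81 |
| 10% | 2.1, 0.89 | 3.2, 0.97 |
| 20% | 4.2, 0.99 | 6.4, >0.99 |

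These figures show what would follow from each assumption. They do not estimate the undercount.

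**The case against.** The strongest reply is that the sentence sits under dose delay and was meant only as a dosing exception. The sections that govern capture and analysis (6.1, 8.1.1, 8.2, 10.4.3) contain no flare exclusion, and a site that follows them would record it. This stands in part: it makes the undercount conditional on sites following 3.4.2. It does not remove the conflict. The other 3.4.2 bullets that excuse events, on laboratory abnormalities and on certain Grade 3 symptoms, speak only of dose delays. The flare bullet alone also withdraws AE status, and nothing elsewhere restores it.

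A reader might infer that flare will certainly be missing from every AE table, or that the rule always lowers the reported rate. The documents do not support either. The first depends on which section a site follows. The second fails for any participant who has another AE of equal or higher grade, whose any-AE and worst-grade counts do not change. Such overlap is plausible: 14.1.2 reports treatment-related events in 67.6% of 630 participants.

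A reader might also infer that, because the tumor lies in the nasal cavity, much drug toxicity would be lost this way. The documents give no rate of pain, irritation or rash at tumor sites. The nasal event with a stated rate is epistaxis (12%, 14.1.2), which falls outside the flare definition. Section 8.1.6 collects mucosal bleeding, and cutaneous lesions possibly due to TGF-beta, as events of special interest regardless of site. These stay captured unless a skin event is labelled flare.

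Finally, the endpoint is secondary and descriptive, with no test or threshold attached. That is correct and limits the weight of the point.

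**Conclusion.** The contradiction is real and lies in the current text. If sites apply 3.4.2, flare at any grade goes unrecorded as an AE and cannot enter the 10.4.3 tables, so the direction of error is fixed: undercounting of local toxicity is possible and overcounting is not.

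The amount cannot be computed. The most that can be said is up to 3.1 to 4.8 points per omitted participant on a flare-specific rate, for denominators of 32 down to 21, and possibly nothing on any-AE rates. This assumes that some flare occurs and that at least some sites or investigators follow 3.4.2 rather than 8.1.1.

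The primary objective response rate, the two-stage interim decision (10.4.5) and the accrual halting rule (3.2) rest on response or progression and are unaffected.

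**What to change.** In the last bullet of 3.4.2, strike the words that deny AE status and leave the words on dose interruption as they stand. Flare is then recorded, graded and attributed under 8.1.1, 6.1 and 8.2, and tabulated by type under 10.4.3, which needs no change.

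Separately, the sponsor must reconcile the dosing statements on flare. The Grade 4 rule in 3.4.1, on "Any Grade 4 or higher adverse drug reactions (ADRs) graded according to NCI CTCAE v5.0", excepts only certain laboratory values, whereas the flare bullet in 3.4.2 rules out interruption without any grade limit. The first bullet of 3.4.2, on withholding drug for attributed toxicity of Grade 2 or higher, also has to be squared with it. No dosing rule is proposed here.

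The cost is a deletion of a few words, slightly more AE recording, and possibly slightly higher reported AE rates.
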